#### **1.2.4 Phase 2 Trial in Atopic Dermatitis Patients Outside Japan (271-12-205)**

In the phase 2 trial in AD patients (aged 10 - 70 years old) outside Japan, the efficacy, safety, and pharmacokinetics of an 8-week twice-daily multiple administrations of OPA-15406 ointment were investigated by selecting 0.3% and 1% formulations (40 subjects for each group) for which the efficacy was suggested in the phase 1 trial in the US, using the vehicle of OPA-15406 ointment (placebo) as the control. The primary efficacy endpoint was established as the incidence of success in IGA (rate of subjects with an IGA score of 0 or 1 with an improvement by at least 2 grades) at Week 4. The incidence of success in IGA was 14.63%, 20.93%, and 2.70% in the 0.3% OPA-15406 group, the 1% OPA-15406 group, and the vehicle group, respectively. The 0.3% OPA-15406 group showed a higher incidence of success in IGA than the vehicle group; however, no significant difference was observed between the groups ( $p = 0.0690$ , CMH test). In the 1% OPA-15406 group, a significant difference was observed in the incidence of success in IGA compared to the vehicle group ( $p = 0.0165$ , CMH test). Discontinuations due to adverse events occurred with 4 subjects (9.8%), 3 subjects (7.0%), and 7 subjects (18.9%) in the 0.3% OPA-15406 group, the 1% OPA-15406 group, and the vehicle group, respectively. In the 0.3% OPA-15406 group, erythema and pruritus that occurred in 1 subject were judged as IMP-related, and cellulitis, dermatitis atopic, and multiple

sclerosis that occurred in 1 subject each were judged as not IMP-related. In the 1% OPA-15406 group, dermatitis atopic in 2 subjects and giardiasis in 1 subject were reported; however, all of these events were judged as not IMP-related. In the vehicle group, dermatitis atopic and application site irritation in 1 subject each were judged as IMP-related, and dermatitis atopic in 2 subjects and pruritus, papule, and excoriation in 1 subject each were judged as not IMP-related. Serious adverse events were reported as liver function test abnormal and multiple sclerosis in 1 subject each in the 0.3% OPA-15406 group and giardiasis and depression in 1 subject each in the 1% OPA-15406 group; however, all of these events were determined as not IMP-related. In the results of clinical laboratory tests, vital signs, and 12-lead ECG, no marked difference was observed among the 3 groups. The plasma OPA-15406 concentrations at 4 hours post-administration at Week 4 were 0.236 to 7.26 ng/mL in 5 subjects in the 0.3% OPA-15406 group and 0.469 to 1.22 ng/mL in 4 subjects in the 1% OPA-15406 group.

#### **1.2.5 Trial for Phototoxicity in Healthy Adult Subjects in the United States (271-12-212)**

In the trial for phototoxicity in 40 healthy adult subjects in the US, the phototoxicity was evaluated by a single administration of 0.3%, 1%, or 3% formulation of OPA-15406 ointment or the corresponding vehicle (placebo) on the back of the subject. At the treatment area, no adverse events were observed. Also, no serious adverse events were reported, and no subjects were withdrawn from the trial due to adverse events.

#### **1.2.6 Trial for Photoallergy in Healthy Adult Subjects in the United States (271-12-213)**

In the trial for photoallergy in 62 healthy adult subjects in the US, photoallergy was evaluated by multiple administrations of 0.3%, 1%, or 3% formulation of OPA-15406 ointment or the corresponding vehicle (placebo) on the back of the subject by establishing a 19-day sensitization period and a 5-day induction period. At the treatment area, erythema was observed in 1 subject as an adverse event, which was moderate in severity and determined as IMP-related. No serious adverse events were reported. One subject discontinued the trial due to the onset of an adverse event, pneumonia; however, a causal relationship with the IMP was ruled out.

### **1.3 Known and Potential Risks and Benefits**

In the phase 1 trial in healthy adults in the US (271-11-202), the trial for phototoxicity in the US (271-12-212), the trial for photoallergy in the US (271-12-213), the phase 1 trial in healthy adult male subjects in Japan (271-14-001), the phase 1 trial in AD patients in

the US (271-12-204), and the phase 2 trial outside Japan (271-12-205), OPA-15406 was administered to 174 healthy adult subjects and 144 AD patients (including 16 patients aged 10 - 17 years old). The longest duration of dosing was 8 weeks.

Commonly reported adverse events in healthy adult subjects receiving OPA-15406 for 4 weeks were application site dermatitis in 26 subjects (14.9%), application site erosion in 13 subjects (7.5%), pruritus in 8 subjects (4.6%), erythema in 7 subjects (4.0%), application site pruritus in 6 subjects (3.4%), application site erythema in 4 subjects (2.3%), headache in 4 subjects (2.3%), abdominal pain in 2 subjects (1.1%), and nausea in 2 subjects (1.1%).

Commonly reported adverse events in AD patients receiving OPA-15406 for 4 or 8 weeks were dermatitis atopic in 19 subjects (13.2%), headache in 7 subjects (4.9%), upper respiratory tract infection in 6 subjects (4.2%), nasopharyngitis in 4 subjects (2.8%), diarrhoea in 3 subjects (2.1%), application site pain in 3 subjects (2.1%), urinary tract infection in 3 subjects (2.1%), pruritus in 3 subjects (2.1%), vomiting in 2 subjects (1.4%), chest discomfort in 2 subjects (1.4%), impetigo in 2 subjects (1.4%), sinusitis in 2 subjects (1.4%), and post inflammatory pigmentation change in 2 subjects (1.4%).

In 271-12-204, application site pain was reported using terms of “application site stinging (mild)” in 1 subject in the OPA-15406 3% group and “application site burning sensation (mild)” in 1 subject in the OPA-15406 1% group. In 271-12-205, application site pain was reported using the term “mild burning sensation after IMP administration (mild)” in 1 subject in the OPA-15406 0.3% group. Regardless of these symptoms, the subjects continued the treatment with OPA-15406 for 8 weeks which was the longest duration of treatment.

In AD patients treated with OPA-15406, 5 serious adverse events (cholelithiasis, giardiasis, liver function test abnormal, multiple sclerosis, and depression) were reported; however, all of these events were judged as not IMP-related by the investigator or the sponsor.

Of the adverse events judged as possibly related or definitely related to OPA-15406 in the overall trials, commonly reported events (in order of incidence) were dermatitis atopic (dermatitis atopic aggravated) (2.8%) and application site pain (2.1%). Other adverse events judged as possibly related or definitely related to OPA-15406 were 1 event (0.7%) each of erythema, pruritus, application site oedema, dry mouth, hypersensitivity, vulvovaginal mycotic infection, and sinusitis. All of these events were mild in severity. Due to the small number of subjects who were enrolled in this trial and included in the

analysis, further evaluation will be required for events that occurred only once and were judged as possibly related to IMP. Therefore, these events should be monitored in detail. The Investigator's Brochure includes other detailed information.

The benefits of participating in the trial include the fact that AD symptoms may improve, and that the subjects could receive more detailed tests and examinations by physicians than they could have with just general examinations. At present, no PDE4 inhibitors to indicate AD have been approved in and outside Japan.

## **2 Trial Rationale and Objectives**

### **2.1 Trial Rationale**

Based on preclinical study results, OPA-15406 is expected to be useful for the treatment of AD; therefore, Otsuka Pharmaceutical Co., Ltd. started development of OPA-15406 ointment from 2011 in the US aiming to obtain approval for the indication of "AD." After completion of the phase 1 trial in healthy adults in the US (271-11-202), the phase 1 trial in AD patients aged 18 to 64 years old was performed in the US (271-12-204) as a proof-of-concept trial. Then, the phase 2 trial in AD patients aged 10 to 70 years old was completed outside Japan (271-12-205) as a dose-finding trial. Currently, a pharmacokinetic trial in AD patients aged 2 to 9 years old has been planned in the US. In Japan, development started from 2014, and the phase 1 trial was performed in healthy adults in Japan (271-14-001). After safety had been demonstrated in healthy Japanese adult subjects, the phase 2 trial in adult AD patients aged 15 to 70 years old to evaluate the safety, efficacy, and pharmacokinetics (271-15-001), and this trial in pediatric AD patients aged 2 to 14 years old to evaluate the safety, efficacy, and pharmacokinetics have both been planned.

In both pediatric and adult patients with AD, abnormalities in the skin barrier function are observed, such as an increased loss of transepidermal water, a decreased content of natural moisturizing factors in the stratum corneum, and a decreased filaggrin content in the stratum corneum. Also, in both pediatric and adult patients, AD is diagnosed based on symptoms of "pruritus," "characteristic rash and its distribution," and "chronic and repeated courses," with no particular difference being found in the pathological nature between pediatric and adult patients with AD. Due to the reduced skin barrier function, AD patients have increased skin irritability against nonspecific stimulants than healthy people, which causes the development of inflammation. Skin inflammation

results in a vicious cycle of further exacerbation of eczema by reduced skin barrier function, increased irritability, and stimulation by scratching. It has been reported that, within a year of birth, infants develop a similar skin barrier function to that of adults. However, infants younger than 2 years old have an incomplete barrier function compared to adults due to physiological differences, such as transepidermal water loss and pH and are likely to develop skin inflammation.

As described above, the pathological conditions of AD do not generally differ depending on age, but infants are still likely to develop skin inflammation. According to the International Conference on Harmonisation (ICH)-E11 (Guidance on Clinical Investigation of Medicinal Products in the Pediatric Population), babies up to 23 months after birth are defined as infants and toddlers, and those aged 2 to 11 years old are defined as children. Therefore, the lower age limit is established as 2 years old in this trial. In the package insert in Japan, children are usually defined as being of an age less than 15 years old. Therefore, in the phase 2 trial (271-15-001) in adult AD patients, the lower age limit was set as 15 years old, and in this trial in pediatric AD patients, the upper age limit has been set as 14 years old.

Prior to start of this trial, a toxicity study was performed using 25-day-old juvenile rats (corresponding to about 2 years old in humans). White petrolatum, OPA-15406 ointment 0% (vehicle), 0.3%, 1%, or 3% was administered to intact skin (open cutaneous) approximately equivalent to 10% of total BSA once daily for 8 weeks in multiple administrations. As a result, no changes associated with the test substance were observed at the application sites in any of the treatment groups. For systemic symptoms, decreased body weight in females of the 1% group, and decreased body weight gain, reduced food consumption, reduced grip strength, and decreased thymus and spleen weights in females of the 3% group were observed; however, these changes resolved after washout. Also in adult animals, decreased body weight gain, reduced food consumption, and decreased thymus and spleen weights were observed, suggesting that these changes were not associated with developmental toxicity specific to juvenile rats. The no observed adverse effect dose level was 3.27 mg/kg/day for males and 1.25 mg/kg/day for females in adult rats (6 weeks old), and 38.52 mg/kg/day for males and 4.23 mg/kg/day for females in juvenile rats (25 days old), revealing that the threshold of toxicity did not decrease in juvenile animals.

In addition, it is known that the brain develops after birth, and that the profile of OPA-15406 is such that it reaches the CNS. Therefore, a 10-week repeated-dose percutaneous

toxicity study was conducted in neonatal rats (4 days old at the start of administration) with a focus on CNS development. No influence of OPA-15406 on the function or structure of the CNS was found.

Based on the clinical trial results obtained so far, the safety of OPA-15406 was discussed by dividing the OPA-15406 group into two age groups of adults  $\geq 18$  years old and juveniles including children from 10 to  $< 18$  years old. Table 2.1-1 shows the serious adverse events. In the adult population, serious adverse events were reported in 4 subjects in the 0.3% and 1% groups; however, its causal relationship with the IMP was ruled out. In the juvenile population, a serious adverse event was reported in 1 subject, and its causal relationship with the IMP was also ruled out. Table 2.1-2 shows the adverse events leading to treatment discontinuation. Adverse events leading to treatment discontinuation are reported in 6 subjects in the 0.3% and 1% groups in the adult population, and 2 subjects in the juvenile population. Table 2.1-3 shows adverse events occurred in at least 2 subjects in either group. The incidence of dermatitis atopic was slightly higher in juvenile subjects of the 0.3% group. Table 2.1-4 presents adverse events possibly related to the IMP. These results showed no marked difference in the incidence between the groups. Based on the above findings, none of the adverse events was specific to the juvenile subjects, and no particular concerns were raised over safety. Also, efficacy was demonstrated in both the phase 1 trial in AD patients aged 18 to 64 years old in the US (271-12-204) and the phase 2 trial in AD patients aged 10 to 70 years old outside Japan (271-12-205).

Table 2.1-1 Serious Adverse Events Reported in the OPA-15406 Group in the Clinical Trials in AD Patients					
	Adult subjects (≥18 years old)			Juvenile subjects (10 to <18 years old)	
System organ class Preferred term	0.3% (N=49) n (%)	1% (N=56) n (%)	3% (N=23) n (%)	0.3% (N=7) n (%)	1% (N=9) n (%)
Total	2 (4.1)	2 (3.6)	0 (0.0)	0 (0.0)	1 (11.1)
Hepatobiliary disorders					
Cholelithiasis	0 (0.0)	1 (1.8)	0 (0.0)	0 (0.0)	0 (0.0)
Infections and infestations					
Giardiasis	0 (0.0)	1 (1.8)	0 (0.0)	0 (0.0)	0 (0.0)
Investigations					
Liver function test abnormal	1 (2.0)	0 (0.0)	0 (0.0)	0 (0.0)	0 (0.0)
Nervous system disorders					
Multiple sclerosis a	1 (2.0)	0 (0.0)	0 (0.0)	0 (0.0)	0 (0.0)
Psychiatric disorders					
Depression b	0 (0.0)	0 (0.0)	0 (0.0)	0 (0.0)	1 (11.1)

The trial results of 271-12-204 and 271-12-205 are combined.

aReported as newly developed multiple sclerosis.

bReported as aggravation of depression.

Table 2.1-2 Adverse Events Leading to Treatment Discontinuation in the OPA-15406 Group in the Clinical Trials in AD Patients					
	Adult subjects (≥18 years old)			Juvenile subjects (10 to <18 years old)	
System organ class Preferred term	0.3% (N=49) n (%)	1% (N=56) n (%)	3% (N=23) n (%)	0.3% (N=7) n (%)	1% (N=9) n (%)
Total	3 (6.1)	3 (5.4)	1 (4.3)	1 (14.3)	1 (11.1)
Immune system disorders					
Hypersensitivity	0 (0.0)	0 (0.0)	1 (4.3)	0 (0.0)	0 (0.0)
Infections and infestations					
Cellulitis	1 (2.0)	0 (0.0)	0 (0.0)	0 (0.0)	0 (0.0)
Giardiasis	0 (0.0)	1 (1.8)	0 (0.0)	0 (0.0)	0 (0.0)
Nervous system disorders					
Multiple sclerosis a	1 (2.0)	0 (0.0)	0 (0.0)	0 (0.0)	0 (0.0)
Psychiatric disorders					
Depression b	0 (0.0)	0 (0.0)	0 (0.0)	0 (0.0)	1 (11.1)
Skin and subcutaneous tissue disorders					
Dermatitis atopic	0 (0.0)	2 (3.6)	0 (0.0)	1 (14.3)	0 (0.0)
Erythema	1 (2.0)	0 (0.0)	0 (0.0)	0 (0.0)	0 (0.0)
Pruritus	1 (2.0)	0 (0.0)	0 (0.0)	0 (0.0)	0 (0.0)

The trial results of 271-12-204 and 271-12-205 are combined.

aReported as newly developed multiple sclerosis.

bReported as aggravation of depression.

Table 2.1-3 Adverse Events Occurred in at Least 2 Subjects in the Clinical Trials in AD Patients					
	Adult subjects (≥18 years old)			Juvenile subjects (10 to <18 years old)	
System organ class Preferred term	0.3% (N=49) n (%)	1% (N=56) n (%)	3% (N=23) n (%)	0.3% (N=7) n (%)	1% (N=9) n (%)
Gastrointestinal disorders					
Dental caries	1 (2.0)	0 (0.0)	0 (0.0)	0 (0.0)	0 (0.0)
Diarrhoea	1 (2.0)	2 (3.6)	0 (0.0)	0 (0.0)	0 (0.0)
Toothache	0 (0.0)	1 (1.8)	0 (0.0)	0 (0.0)	0 (0.0)
Vomiting	0 (0.0)	2 (3.6)	0 (0.0)	0 (0.0)	0 (0.0)
General disorders and administration site conditions					
Application site pain	1 (2.0) a	1 (1.8) b	1 (4.3) c	0 (0.0)	0 (0.0)
Chest discomfort	0 (0.0)	2 (3.6)	0 (0.0)	0 (0.0)	0 (0.0)
Infections and infestations					
Cellulitis	1 (2.0)	0 (0.0)	0 (0.0)	0 (0.0)	0 (0.0)
Impetigo	0 (0.0)	2 (3.6)	0 (0.0)	0 (0.0)	0 (0.0)
Nasopharyngitis	2 (4.1)	1 (1.8)	0 (0.0)	1 (14.3)	0 (0.0)
Sinusitis	1 (2.0)	1 (1.8)	0 (0.0)	0 (0.0)	0 (0.0)
Upper respiratory tract infection	3 (6.1)	1 (1.8)	0 (0.0)	2 (28.6)	0 (0.0)
Urinary tract infection	2 (4.1)	0 (0.0)	1 (4.3)	0 (0.0)	0 (0.0)
Nervous system disorders					
Headache	2 (4.1)	2 (3.6)	1 (4.3)	1 (14.3)	1 (11.1)
Skin and subcutaneous tissue disorders					
Dermatitis atopic	8 (16.3)	6 (10.7)	1 (4.3)	3 (42.9)	1 (11.1)
Erythema	1 (2.0)	0 (0.0)	0 (0.0)	0 (0.0)	0 (0.0)
Post inflammatory pigmentation change	1 (2.0)	1 (1.8)	0 (0.0)	0 (0.0)	0 (0.0)
Pruritus	3 (6.1)	0 (0.0)	0 (0.0)	0 (0.0)	0 (0.0)

The trial results of 271-12-204 and 271-12-205 are combined. Adverse events occurring in at least 2 subjects in the OPA-15406 group, or adverse events occurring in 1 subject in the OPA-15406 group and in at least 2 subjects in a combined group of the tacrolimus group or vehicle group are shown.

aTerm used by the reporter: Mild burning sensation after IMP administration (mild)

bTerm used by the reporter: Application site burning sensation (mild)

cTerm used by the reporter: Application site stinging (mild)

Table 2.1-4 Adverse Events Possibly Related to the Trial Treatment in the OPA-15406 Group in the Completed Trials of OPA-15406 in AD Patients					
	Adult subjects (≥18 years old)			Juvenile subjects (10 to <18 years old)	
System organ class Preferred term	0.3% (N=49) n (%)	1% (N=56) n (%)	3% (N=23) n (%)	0.3% (N=7) n (%)	1% (N=9) n (%)
Total	4 (8.2)	3 (5.4)	4 (17.4)	2 (28.6)	0 (0.0)
Gastrointestinal disorders					
Dry mouth	0 (0.0)	0 (0.0)	1 (4.3)	0 (0.0)	0 (0.0)
General disorders and administration site conditions					
Application site oedema	0 (0.0)	1 (1.8)	0 (0.0)	0 (0.0)	0 (0.0)
Application site pain	1 (2.0) a	1 (1.8) b	1 (4.3) c	0 (0.0)	0 (0.0)
Immune system disorders					
Hypersensitivity	0 (0.0)	0 (0.0)	1 (4.3)	0 (0.0)	0 (0.0)
Infections and infestations					
Sinusitis	1 (2.0)	0 (0.0)	0 (0.0)	0 (0.0)	0 (0.0)
Vulvovaginal mycotic infection	0 (0.0)	1 (1.8)	0 (0.0)	0 (0.0)	0 (0.0)
Skin and subcutaneous tissue disorders					
Dermatitis atopic	1 (2.0)	0 (0.0)	1 (4.3)	2 (28.6)	0 (0.0)
Erythema	1 (2.0)	0 (0.0)	0 (0.0)	0 (0.0)	0 (0.0)
Pruritus	1 (2.0)	0 (0.0)	0 (0.0)	0 (0.0)	0 (0.0)

The trial results of 271-12-204 and 271-12-205 are combined.

aTerm used by the reporter: Mild burning sensation after IMP administration (mild)

bTerm used by the reporter: Application site burning sensation (mild)

cTerm used by the reporter: Application site stinging (mild)

Based on the above findings, it was judged scientifically and ethically appropriate to conduct this trial in order to evaluate the safety, efficacy, and pharmacokinetics of OPA-15406 in children aged 2 to 14 years old, in consideration of the standard age classification in ICH-E11 and the package insert, and that no particular concerns over safety in juvenile animals corresponding to newborns to 2-year-old human infants in the nonclinical studies, and no marked concerns over safety and suggested efficacy in the clinical trials in AD patients aged 10 to <18 years old including children were observed.

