In an 8-week repeated-dose percutaneous toxicity study in juvenile rats (25 days old at the start of administration), white petrolatum 0% (vehicle), OPA-15406 ointment 0.3% (male: 3.76 mg/kg, female: 4.23 mg/kg), 1% (male: 12.56 mg/kg, female: 14.32 mg/kg), or 3% (male: 38.52 mg/kg, female: 43.83 mg/kg) was administered once daily to intact skin (open cutaneous) approximately equivalent to 10% of total BSA. As a result, no changes associated with the test substance were observed on the administration sites in any of the treatment groups. Although suppressed weight increase and reductions in food intake and grip strength were observed in female rats with 1% or 3% ointment, these changes were not developmental toxicity and they resolved with washout. Also, there was no difference in the toxicity threshold between adult and juvenile rats. As the profile of OPA-15406 is such that it reaches the central nervous system (CNS) and the brain is known to develop after birth, a 10-week repeated-dose percutaneous toxicity study was conducted in neonatal rats (4 days old at the start of administration) with a focus on CNS development, but no influence of OPA-15406 on the function or structure of the CNS was found.

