### **3.7 Trial Procedures**

The schedule of assessments is shown in Table 3.7-1. Items that clinical trial associates are capable of performing may be performed by the clinical trial associates under the supervision of the investigator.

Table 3.7-1 Schedule of Assessments							
Assessment	Screening period (2-30 days)	Assessment period (4 weeks)					Post-treatment observation period (2 weeks)
	Screening examination	Baseline examination	Week 1 examination a (± 2 days)	Week 2 examination b (± 3 days)	Week 4 examination b (± 3 days) Withdrawal examination d	Unscheduled visit	Examination 2 weeks after the last IMP administration c (± 7 days)
Informed consent	○						
Inclusion/exclusion criteria	○	○					
Subject demographics	○						
Physical findings	○	○	○	○	○	○ e	○
Vital signs (including body weight)	○	○	○	○	○	○ e	
12-lead ECG f	○				○	○ e	
Clinical laboratory tests	○				○	○ e	
Pregnancy test g	○				○	○ e	
IGA	○	○	○	○	○		
EASI		○	○	○	○		
VAS for pruritus h		○	○	○	○		
VRS for pruritus h		○ i	← → ○				
POEM		○	○	○	○		
Affected BSA	○	○	○	○	○	○	
Treatment area		○	○	○		○	
Blood sampling for plasma drug concentration measurement			○ j		○ k		
Administration diary		○ l	← →		○		
Severity of AD		○					
Status of IMP Administration			○	○	○		
Prescription and return of IMP		○ m	○ n	○	○ o	○ n	
IMP administration		○ p	← →				

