#### **3.7.1.9 Examination 2 Weeks After Last IMP Administration ( $\pm 7$ Days)**

The investigator or subinvestigator will perform the following examinations, observations, and evaluations and record the results in the source document and CRF.

- Physical examination
- Adverse events

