6.4 Study Week Windows

The definitions of timepoints for analysis are described in Table 6.4-1 and Table 6.4-2. Timepoints, including unscheduled visits and visit at discontinuation, will be determined based on the number of days from the start of IMP administration. However, for Verbal Rating Scale (VRS), the timepoint will be determined based on the amount of time that has elapsed from the start of IMP administration. For efficacy variables, the data obtained between the day of the start of IMP administration and 7 days after the last IMP administration will be used in analyses. If multiple data exist within the allowable window of the timepoint, the data obtained last will be used for analyses. Data for the Last Visit will be defined as the last data obtained between the day of the start of IMP administration and 7 days after the last IMP administration (including data obtained at discontinuation) for efficacy variables or as the last data obtained after the start of the IMP administration for safety variables.

In analyses, baseline data will be defined as data obtained on the day or at the date and time before and nearest to the start of IMP administration, including the screening data.

Table 6.4-1 Timepoints and Allowable Windows for Efficacy Variables (Except VRS) and Safety Variables				
Timepoint	Study Day	Allowable Window (Days After the Start of IMP Administration)		
Week 1	8	1	-	10
Week 2	15	11	-	21
Week 4	29	22	-	43

Table 6.4-2 Timepoints and Allowable Windows for VRS			
Timepoint	Allowable Window (Hours After the Start of IMP Administration)		
Hour 4	1	-	< 6
Hour 8	6	-	< 10
Hour 12	10	-	< 18
Hour 24	18	-	< 30
Hour 36	30	-	< 42
Hour 48	42	-	< 54
Hour 60	54	-	< 66
Hour 72	66	-	< 78
Hour 84	78	-	< 90
Hour 96	90	-	< 102
Hour 108	102	-	< 114
Hour 120	114	-	< 126
Hour 132	126	-	< 138
Hour 144	138	-	< 150
Hour 156	150	-	< 162
Hour 168	162	-	< 174

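### No body weight is scheduled at the visit 2 weeks after treatment, although reversal after washout is one of the reasons given for discounting the weight finding in juvenile rats

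*Protocol*

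**What the plan says.** **The animal finding.** Protocol Section 2.1 describes an 8-week study in juvenile rats. It reports "decreased body weight in females of the 1% group". At 3% in females it adds slower weight gain, lower food intake, weaker grip and lighter thymus and spleen. The sentence closes "in females of the 3% group were observed; however, these changes resolved after washout". Two more reasons follow. Similar changes occurred in adult animals, "suggesting that these changes were not associated with developmental toxicity specific to juvenile rats", and the no-effect doses are compared, "revealing that the threshold of toxicity did not decrease in juvenile animals". Section 1.1 repeats the conclusion: "these changes were not developmental toxicity and they resolved with washout". Sections 1.1 and 3.4.2, however, describe the finding at 1% or 3% as a slowing of weight gain, not a fall in weight.

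**The trial schedule.** Body weight belongs to vital signs (Section 3.7.5.4). In Table 3.7-1 the row that begins "Vital signs (including body weight" is marked from screening to Week 4 or withdrawal, and with a footnote for unscheduled visits. It has no mark in the post-treatment column. Section 3.7.1.9, "Examination 2 Weeks After Last IMP Administration", lists two items only: physical examination and adverse events. Section 3.7.5.3 defines the physical examination without weighing.

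**The SAP.** Section 9.6 summarises weight at each timepoint, and Section 6.4 defines Weeks 1, 2 and 4 only. Table 16.1-1 has a criterion of a 7% weight change. Section 9.6 does not name weight among the variables for which potentially clinically significant counts are made.

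**The concern.** Safety in children from age 2 is the primary objective. Body weight changed in juvenile animals at a concentration used here, and the protocol's answer includes the observation that the change went away off treatment. The trial already brings every child back about 2 weeks after the last application, and it has a randomised vehicle arm for comparison, yet it does not take the one measurement that would bear on that observation.

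What is at stake is limited. A weight effect on treatment would still be seen up to Week 4. If one appeared, the study report could not say from planned data whether it had begun to reverse.

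**Working it through.** The plan gives no figure to reproduce on this point. The check compares sections and adds some simple arithmetic.

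**1. Count the scheduled weights.** Screening, baseline, Week 1, Week 2, and Week 4 or withdrawal make 5. None is off treatment. Other routes to a later weight:
- Unscheduled visits (3.7.1.10) are prompted by marked enlargement of the affected area, and vital signs are optional there.
- Adverse event follow-up (3.1 and 5.8.1) applies only if the change was reported as an event. It prescribes no re-weighing, and information obtained after the 2-week visit goes to medical records.

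**2. Put the dose in context.** Section 1.1 gives 14.32 mg/kg for juvenile females at 1%. Section 2.1 gives 4.23 mg/kg/day as their no-effect level. The ratio is 14.32 / 4.23 = 3.39, so the 1% group was above that level in the rat study.

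For a child, Section 3.2.1 leads to: applied dose at 1% = BSA × treatment area × 10 g/m² × 2 per day × 10 mg/g ÷ weight, with BSA = √(height × weight / 3600). The documents give no body sizes, so these are assumed:
- 80 cm, 10 kg (BSA 0.471 m²): 0.47 mg/kg/day at 5% area, 3.77 at 40%
- 105 cm, 17 kg (0.704 m²): 0.41 and 3.31
- 155 cm, 45 kg (1.392 m²): 0.31 and 2.47

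All are below 4.23. The 40% figures are above the 1.25 mg/kg/day that Section 2.1 gives for adult female rats; the 5% figures are not. These are applied doses, not systemic exposure.

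**3. Place the visit on the SAP time axis.** With the last application at about Day 28 ± 3 (Days 25 to 31), a visit 14 ± 7 days later falls between Day 25 + 7 = 32 and Day 31 + 21 = 52. The Week 4 window is Days 22 to 43, and SAP 6.4 says: "If multiple data exist within the allowable window of the timepoint, the data obtained last will be used for analyses". A post-treatment weight taken by Day 43 would therefore replace the Week 4 weight. The safety definition of Last Visit would also take it, because the limit of 7 days after the last application applies to efficacy variables only.

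**4. Ask what the extra weight could show.**
- One child: 7% of an assumed 12 kg is 0.84 kg. Weight is recorded to 0.1 kg, so recovery in an individual would be readable.
- Arm against vehicle, 20 per arm, assumed SD of the off-treatment change 0.3 to 0.6 kg: half-width = t(0.975, 38) × SD × √(2/20) = 2.024 × SD × 0.316. This gives 0.19 kg for SD 0.3 and 0.38 kg for SD 0.6.

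**The case against.** Four stronger readings are tempting, and the documents support none of them.

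- *That the protocol accepts the finding because it reversed.* Reversal is one of three reasons in Section 2.1, which also draws on clinical data from patients aged 10 to under 18.
- *That children receive the dose that lowered weight in rats.* The concentration is the same, but the applied dose per kilogram is lower, and it is below the juvenile female no-effect level under the assumed sizes. Nor do the documents rank weight as the main effect.
- *That reversal could never be seen.* A reported adverse event is reviewed at the 2-week visit and followed until it resolves or stabilises. What is missing is a scheduled measurement.
- *That a child losing 7% is flagged at Week 4 and then dropped.* SAP 9.6 does not clearly produce that flag at all.

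The other side can add that reversibility is neither an objective nor an endpoint, that laboratory tests and ECG are not repeated off treatment either, and that an extra weight would be hard to attribute. Time off treatment would run from 7 to 21 days, and children grow. The restrictions in protocol Section 4.1 end at the Week 4 examination, and that section requires drugs to be recorded only up to then. If the rat effect was slower gain, a 7% fall is also an insensitive yardstick.

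All of this stands as a limit on interpretation. It does not remove the value of an off-treatment weight with a concurrent vehicle arm. Growth and the visit window should affect the arms alike on average; treatment started after Week 4 need not.

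**Conclusion.** The gap is real and modest. The plan has no scheduled weight after treatment stops, so it has no planned data on the reversal of a weight change. This is an inexpensive improvement in the domain of the primary objective. It is not a contradiction in the documents and not evidence of risk to the children.

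Two related inconsistencies are matters of wording and should be settled at the same time: fall in weight (Section 2.1) against slower gain (Sections 1.1 and 3.4.2), and the 7% weight criterion in SAP Table 16.1-1 that SAP 9.6 leaves out.

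The dose comparison depends on assumed heights and weights, and the precision on an assumed SD; neither comes from the documents. The count of zero scheduled off-treatment weights needs no assumption.

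**What to change.** **Protocol**
- Add body weight to Section 3.7.1.9 and to the post-treatment column of Table 3.7-1.
- Reconcile how Sections 1.1, 2.1 and 3.4.2 describe the juvenile finding at 1%.

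**SAP 6.4**
- Give this weight a separate post-treatment timepoint, excluded from the Week 4 window (Days 22 to 43) and from the safety Last Visit. Define it by the visit rather than by day number. A child whose last application was on Day 5, for example, would have the visit between Days 12 and 26, inside the Week 2 or Week 4 window.

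**SAP 9.6**
- Add weight to the potentially clinically significant counts, to match Table 16.1-1.
- Summarise the change from the last on-treatment weight to post-treatment by arm against vehicle, as percent change or by age group, because a mean in kilograms across ages 2 to 14 is hard to read.
- List that change for each child with a decrease of 7% or more.
- State that the summary is descriptive, for the reasons of visit timing, growth and later treatment.

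**Cost.** One measurement at an existing visit, one CRF field, one SAP timepoint and a protocol amendment. No treatment rule changes.
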